2.4.2 Non-inclusion criteria

1. Subjects who are unwilling or unable to provide a signed informed consent form;
2. Any contraindication to the treatment with the SPC of amlodipine/atorvastatin/perindopril according to its' approved instruction for medical use in the Russian Federation;
3. Concomitant use of any other ACE inhibitors, CCBs, ARBs and statins.
4. Supposed low treatment adherence to the assigned SPC and the risk for poor collaboration between the patient and the investigator during the study;
5. Any severe, decompensated or unstable somatic diseases or states that according to investigator discretion are life-threatening or worsen the prognosis for the patient: myocardial infarction in the past 3 months, unstable angina, current decompensation of diabetes mellitus, autoimmune or oncological diseases, severe cardiac arrhythmia,

gastrointestinal disorders affecting absorption, severe hepatic diseases, pancreatic diseases, severe allergic reactions, connective tissue diseases etc;

6. Secondary arterial hypertension;
7. Alcohol or any drug abuse;
8. Surgical intervention on heart or coronary vessels (i.e., heart valve(s) replacement, stent implantation or CABG), or any non-cardiological serious surgical intervention that are planned within next 3 months and may require withdrawal or changes in current therapy;
9. Glomerular filtration rate less than 60 ml/min/1,72m²;
10. Participating in any other clinical trial currently or during 30 days period before informed consent was signed.

2.5 Therapeutic strategy during the study

2.5.1 Treatment with the studied drug

Amlodipine 5 mg + atorvastatin 10 mg + perindopril arginine 5 mg

Amlodipine 5 mg + atorvastatin 20 mg + perindopril arginine 5 mg

Amlodipine 5 mg + atorvastatin 20 mg + perindopril arginine 10 mg

This is non-interventional study that is observational by its nature. Therefore there will be no any assignments of subjects to a particular therapeutic strategies defined by this protocol. Decision to treat a patient with SPC of amlodipine/ atorvastatin/ perindopril should be at the discretion of a treating investigator and made in accordance to local standards and protocols.

2.5.2 Concomitant drugs

Due to the non-interventional design of the study, it is allowed to use any concomitant treatments or drugs if it is considered necessary by the treating investigator. Any changes in the medical treatment are also allowed during the observational period of the study and will be gathered and appropriately reflected in the study documentation at appointed visits to clinics by a treating investigator.

2.6 Duration of non-interventional study

It is planned to complete enrolment of patients in this non-intervention study within 6 months.

Follow-up period for each patient will be 12 weeks.

First patient in is scheduled for Q4 2022

Last patient in is scheduled for Q2 2023

Last patient last visit Q3 2023

Data base lock is scheduled for Q3 2023

Statistical analysis is scheduled for Q4 2023

Clinical study report is scheduled for Q1 2024

2.7 Documentation of the non-interventional clinical study

2.7.1. Documentation folder

Each doctor will be provided with a documentation folder containing a complete set of documents for 5-6 patients + 2 extra sets in case of lost or damage of study documents including:

- One protocol of the observation plan;
- Documents for 5-6 patients (12 *Patient Informed Consent Forms*, with 5-6 *Adverse event/adverse drug reaction/special situation reporting forms*).
- 2 extra sets in case of lost or damage of study documents (*Patient Informed Consent Form*,; *Adverse event/adverse drug reaction/special situation reporting forms*)

2.7.2 Study schedule and plan

According to the design of this multicentre, non-intervention, observational study in patients with HTN and dyslipidemia treated with SPC of amlodipine/atorvastatin/perindopril, three visits will be appointed to include patients and to gather parameters of interest to describe treatment effectiveness and safety of the FDC.

Following visits will be appointed:

1. Inclusion Visit 0 (V0) – month 0;
2. Follow up Visit 1 (V1) – 4 weeks after V0;
3. Final Visit 2 (V2): 12 weeks after V0;

Table 1 – Planned study visits

Procedure	Retrospective evaluation of patient's eligibility	Inclusion Visit 0 Month 0	Follow up visit V1 (4 weeks ± 2 weeks)	Final visit V2 (12 weeks ± 2 weeks)
Written informed consent		×		
Assessment in accordance with inclusion/ non-inclusion criteria	×	×		
Demographics		×		
Risk factors and life style		×		
Cardio-vascular disease history		×		
Physical examination with the measurement of BP at rest		×	×	×

LDL-C		×		×
Current treatment with concomitant cardiovascular medications/ changes and reasons		×	×	×
Current treatment with other concomitant medications		×	×	×
Medication adherence scale		×	×	×
Quality of life evaluation (SF-36)		×	×	×
Treatment with the SPC amlodipine/atorvastatin/perindopril status		×	×	×
SPC amlodipine/atorvastatin/perindopril dosage correction (if occurred)		×	×	×
Adverse events/drug reactions/special situations reporting		×	×	×

2.7.4. Data collection:

Data evaluation during the screening period:

HCPs participating in the study will conduct a retrospective analysis of patient's records for the purpose of evaluating patient's eligibility to be enrolled in the study. Patients with HTN and dyslipidemia who had been initiated with SPC amlodipine/atorvastatin/perindopril within one month before the Index Date and who meet other inclusion / non inclusion criteria will be included in the study if they sign a consent form at the inclusion visit.

Data collection at the inclusion visit (V0):

- Obtaining patient informed consent;
- Checking for inclusion/non-inclusion criteria;
- Demographics, CVD history, cardiovascular risk factors (appendix 8)
- Physical examination and vital signs (BP);
- Current status of taking SPC amlodipine/atorvastatin/perindopril and dose regimen;
- SBP, DBP and LDL-C according to the medical records dated with the nearest to the start of treatment with SPC amlodipine/atorvastatin/perindopril;
- Concomitant current use of any other cardiovascular medications (i.e. antihypertensive, anti-ischaemic, anti-platelet, anticoagulant medications) and any other concomitant medications
- Baseline assessment of adherence to SPC amlodipine/atorvastatin/perindopril done by medication adherence scale;

- Quality of life assessment (questionnaire SF-36)
- Adverse events/drug reactions/special situations

Data collection at the Follow up Visit (V1):

- Physical examination and vital signs (BP);
- Current status of taking SPC amlodipine/atorvastatin/perindopril and dose regimen correction if needed;
- Assessment of adherence to SPC amlodipine/atorvastatin/perindopril done by medication adherence scale;
- Quality of life assessment (questionnaire SF-36)
- Concomitant current use of other cardiovascular medications and any other medications
- Adverse events/drug reactions/special situations

Data collection at the Final Visit (V2):

- Physical examination and vital signs (BP);
- Current status of taking SPC amlodipine/atorvastatin/perindopril and a dose regimen correction if needed;
- LDL-C assessment;
- Assessment of adherence to SPC amlodipine/atorvastatin/perindopril done by medication adherence scale;
- Quality of life assessment (questionnaire SF-36)
- Concomitant current use of other cardiovascular medications and any other medications
- Adverse events/drug reactions/special situations

[figure not shown]

Figure 1. The scheme of TARGET study

2.7.5 Implementation of non-intervention study

The treating investigator will receive a documentation folder and instructions from the Servier staff. The patient should be informed of his/her participation in this study and the transfer of his/her clinical data from the site to the responsible professional subcontractor for statistical analyses. Written informed consent must be obtained from the patient at the inclusion visit.. In case of occurrence of adverse events (AEs), adverse drug reactions (ARDs), or special situations, it is necessary to follow the requirements listed in the section «*Responsibilities of the investigator*». Please hand over the folder with the complete documentation to your Servier local executive.

Patients will undergo clinical assessment and receive the standard medical care as usual determined by the treating doctors based on their clinical judgement and national guidelines. Patients will not receive experimental treatment as a consequence of their participation in the observational study

3 Pharmacovigilance

3.1 Definitions

3.1.1 Pharmacovigilance information

Pharmacovigilance data include any unintended or adverse event associated with the use of a medicinal product in humans, whether or not considered drug related, including the following special situations (situations where no adverse event occurred but information needs to be collected):

- exposure during pregnancy or breastfeeding;
- overdose, abuse, misuse, off-label uses, medication error, or occupational exposure (including professional one);
- lack of treatment effectiveness of a medicinal product;
- any suspected transmission via medicinal product of an infection agent;
- unintended therapeutic benefit.

3.1.2 Adverse Event (AE)

Adverse event is any untoward medical occurrence in a patient or a clinical-trial subject who received the medicinal product, which does not necessarily have a causal relationship with the use of this medicinal product.

An adverse event can therefore be any unfavourable and unintended sign (e.g. an abnormal laboratory finding), symptom, or disease temporally associated with the use of a medicinal product, whether or not considered related to the medicinal product.

3.1.3 Adverse (drug) reaction (ADR)

Adverse reaction (synonyms: Adverse drug reaction, Suspected adverse (drug) reaction, Adverse effect, Undesirable effect) is a response to a medicinal product which is noxious and unintended.

“Response” in this context means that a causal relationship between a medicinal product and an adverse event is at least a reasonable possibility.

Adverse reactions may arise from use of the product within or outside the terms of the marketing authorization or from occupational exposure. Conditions of use outside the marketing authorization include off-label use, overdose, misuse, abuse and medication errors.

3.1.4 Serious adverse (drug) reaction (SADR)

Serious adverse reaction is an adverse reaction, which results in death, is life-threatening, requires in-patient hospitalisation or prolongation of existing hospitalisation, results in persistent or significant disability or incapacity, or is a congenital anomaly/birth defect.

“Life threatening” in this context refers to a reaction in which the patient was at risk of death at the time of the reaction; it does not refer to a reaction that hypothetically might have caused death if more severe.

Medical and scientific judgement should be exercised in deciding whether other situations should be considered serious reactions, such as important medical events that might not be immediately life threatening or result in death or hospitalisation but might jeopardise the patient or might require intervention to prevent one of the other outcomes listed above.

Examples of such events are intensive treatment in an emergency room or at home for allergic bronchospasm, blood dyscrasias or convulsions that do not result in hospitalisation or development of dependency or abuse.

Any suspected transmission via a medicinal product of an infectious agent is also considered a serious adverse reaction.

3.2 Responsibilities

3.2.1 Events to be reported

All available information about the following reported events occurring during the study will be recorded. All reported AEs/ADRs will be described in the statistical analysis report.

- All serious adverse drug reactions related to the use of amlodipine/atorvastatin/perindopril FDC;
- All non-serious adverse drug reactions related to the use of SPC amlodipine/atorvastatin/perindopril);
- All reports about special situations (see 3.1.1);

- All adverse events

3.2.2 Responsibilities of the investigator

At the visits during the study, the treating physician will ask the participating patient to indicate whether or not an adverse event (serious or not) has occurred.

The treating physician should determine the presence/absence of a causal relationship between the use of the study drug and the adverse event, the presence/absence of criteria for seriousness, and then the outcome of the event.

In case of detection of any adverse event/adverse drug reaction or occurrence of a special situation during the study (both serious or not serious), the treating physician must fill out the «*Adverse event/adverse drug reaction/special situation reporting form*» (Appendix No.4) without waiting for the clinical outcome or the results of additional investigations.

If the event is serious, the form should be sent immediately (same or next working day at the latest) to Servier company in Russia via e-mail to address [contact] or by fax to number [name]. The anonymized copies of all the available and relevant laboratory findings, hospitalisation reports or other investigation results performed in relation to the adverse event should be attached to the form. All other events should be transmitted by the treating physician within 2 working days.

The same obligations will apply for follow-up reports. The treating physician must ensure that follow-up of the participant is appropriate to the nature of the event, and that it continues until resolution. She/he will continue to notify follow up data according to timeframes defined above.

If the follow-up of the participant is not done by the treating physician him/herself (hospitalisation, followed by a specialist or the participant's general practitioner,...), the treating physician will do every effort to establish/maintain contact with the person/department in charge of follow-up of the participant, so as to have additional information and report it.

3.2.3 Responsibilities of the Sponsor/Marketing Authorisation Holder

Independently of the regulatory obligations of investigator, the sponsor/marketing authorisation holder (MAH) must report the pharmacovigilance data to the appropriate authorities in accordance with the Good Pharmacovigilance Practice and local regulations.

Cases of adverse event are considered to be closed when the patient has recovered or his/her condition was stabilised, providing that the available data are sufficiently detailed for adequate medical analysis of the case.

4 Data management, quality management, statistics and reporting

4.1 Data management

Data collection in this study is carried out using documentation forms. Centralized data entry will be carried out by a responsible professional subcontractor for statistical analyses after receiving documentation forms. Statistical analysis of the data and the creation of the final statistical report on the study will also be carried out by the responsible professional subcontractor for statistical analyses.

4.2 Statistical analysis

Due to the non-interventional nature of this study, statistical analysis will be carried out in descriptive and exploratory forms. All parameters will be analysed using descriptive statistics. For each parameter, the following will be specified: number of patients, mean value, standard error, minimum and maximum values, or proportion of each category. All composite endpoints will be listed and presented in visual form as graphs and in tables of parameters and their frequencies. For categorical variables, absolute values and rates in per cents be calculated. The calculations of relative rates will include only patients in whom values of the corresponding variables will be available.

Accepted level of significance

In all tests, a significance level of 0.05 will be used, and 2-sided statistical tests will be carried out.

Search statistical analysis will be performed in the following subgroups of patients:

- patients with stable CAD
- patients with diabetes mellitus type 1 or type 2
- patients with chronic kidney disease

All reports of adverse drug reactions (ARDs), adverse events (AEs), serious ADR/AE, and special situations will be encoded using MedDRA by the subcontractor, and the results will be listed and classified according to the System-Organ-Classes (SOCs). Descriptive statistics will be used.

4.3 Report preparation

The preparation of the final report on the study will begin after the completion of the statistical analysis. The publication of the main results is planned within 12 months after the end of the study.

5. Ethical considerations

The study will be carried out in accordance with the principles of the Helsinki Declaration, according to the version revised in Brazil in 2013. The protocol must be reviewed and approved by an independent ethics committee after it is submitted by the coordinator or sponsor in accordance with local regulatory requirements, especially on the matters relating to data protection. Patients will be informed about the conditions for participation in the study, and they will have to provide written consent to participate in the study. The doctor must confirm in the Case report form (CRF) that the informed consent has been obtained, and he/she must keep one

original of the signed informed consent form in the patient's file. "Informed consent" also means an individual discussion of procedures, that will be conducted as a part of the study, with the patient.

5.1 Patient data privacy

Investigators should maintain confidentiality of information about patients included in this study. Confidential data should contain enough information to contact the patient in case of emergency, or if further monitoring is required. Patient's right to privacy is of utmost importance. To protect the data confidentiality and preserve patient anonymity, patient's identity will be encoded in the study documentation. Patients can be identified using a unique number, age and gender, which will be recorded in the CRF. To reveal the patient's identity, all investigators will keep a confidential list for patient identification containing the names and addresses of the patients, as well as their assigned numbers. Thus, only investigator will be able to decode the identity of a patient.

6. Appendices

Appendix 1. Classification of blood pressure and definition of hypertension grade [15].

BP categories	SBP, mm Hg		DBP, mm Hg
Optimal	<120	and	<80
Normal	120–129	and/or	80–84
High normal	130–139	and/or	85–89
Grade 1	140–159	and/or	90–99
Grade 2	160–179	and/or	100–109
Grade 3	≥180	and/or	≥110
Isolated systolic hypertension ¹	≥140	and	<90

¹ Isolated systolic hypertension (ISH) should be classified into grades 1, 2, and 3 according to the SBP level.

Appendix 2.

Medication Adherence Scale [20].

1. Sometimes I can make a break in my daily medication therapy for:
 - a) One day
 - b) Two days
 - c) Three days
 - d) I don't make breaks at all
2. I take my medications:
 - a) Every day
 - b) Only when I feel unwell
 - c) I take courses of medication treatment
 - d) In exceptional cases
3. I change dosage/frequency of medication administered by the doctor:
 - a) I start taking medications as administered and then I change as I feel appropriate
 - b) I make the dosage lower when I feel better
 - c) I change the dosage (make it higher or lower) depending on the way I feel
 - d) I take the dosage administered by the doctor independently of how I feel
4. I stop taking medication when:
 - a) I feel that I am not sick anymore
 - b) I don't feel pain or discomfort anymore
 - c) Medication is withdrawn by the doctor
 - d) Medication doesn't help me

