1.2 Objectives

Primary objective is to describe antihypertensive and hypolipidaemic effectiveness of a triple single-pill combination of amlodipine, atorvastatin and perindopril at 12 weeks in patients with arterial hypertension (HTN) and dyslipidemia in the daily clinical practice.

Secondary objectives

- To determine the proportion of patients who reached systolic (SBP) and diastolic blood pressure (DBP) target goals at weeks 4 and 12 of the observation period respectively.
- To determine the proportion of patients who reached LDL-C target goals at week 12 of the observation period.
- To evaluate the quality of life of patients at visit 1 (V1) and visit 2 (V2) as compared to visit 0 (V0) respectively.
- To evaluate the adherence to treatment with the fixed dose combination (FDC) of amlodipine/atorvastatin/perindopril in patients included into the study at V1 and V2 as compared to V0.
- To evaluate predictors of reaching BP and LDL-C target goals in the study population.

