- Proportion of patients aged 18-64 years at high CV risk who reached SBP <130 and \geq 120 mm Hg and DBP between 70 and79 mm Hg at week 12 of the observation period in the subgroups of patients receiving SPC of amlodipine/atorvastatin/perindopril in the following dosages 5;20;5 mg and 5;20;10 mg and 5;10;5 mg respectively;
- Proportion of patients older than 65 years at high CV risk who reached SBP \leq 139 and \geq 130 mm Hg and DBP between 70 and79 mm Hg at week 12 of the observational period in the subgroups of patients receiving SPC of amlodipine/atorvastatin/perindopril in the following dosages 5;20;5 mg and 5;20;10 mg and 5;10;5 mg respectively;

- Proportion of patients at high CV risk who reached decrease of LDL-C from BL $\geq 50\%$ and reached target $<1,8$ mmol/l (55 mg/dl) at week 12 of the observation period in the subgroups of patients receiving SPC of amlodipine/atorvastatin/perindopril in the following dosages 5;20;5 mg and 5;20;10 mg and 5;10;5 mg respectively;
- Proportion of patients aged 18-64 years at moderate CV risk who reached SBP <130 and ≥ 120 mm Hg and DBP between 70 and 79 mm Hg at week 12 of observational period in the subgroups of patients receiving SPC of amlodipine/atorvastatin/perindopril in the following dosages 5;20;5 mg and 5;20;10 mg and 5;10;5 mg respectively;
- Proportion of patients older than 65 years at moderate CV risk who reached SBP ≤ 139 and ≥ 130 mm Hg and DBP between 70 and 79 mm Hg at week 12 of the observation period in the subgroups of patients receiving SPC of amlodipine/atorvastatin/perindopril in the following dosages 5;20;5 mg and 5;20;10 mg and 5;10;5 mg respectively;
- Proportion of patients at moderate CV risk who reached LDL-C $< 2,6$ mmol/l (100 mg/dl) at week 12 of the observation period in the subgroups of patients receiving SPC of amlodipine/atorvastatin/perindopril in the following dosages 5;20;5 mg and 5;20;10 mg and 5;10;5 mg respectively;
- Mean change from V0 in scores of the SF-36 questionnaire assessed at V1 and V2;
- Proportion of patients with high, moderate and low adherence to the treatment with SPC of amlodipine/atorvastatin/perindopril at V1 as compared to V0 via medication adherence scale;
- Proportion of patients with high, moderate and low adherence to the treatment with SPC of amlodipine/atorvastatin/perindopril at V2 as compared to V0 via medication adherence scale;
- Association between the fact of achieving target BP levels at week 12 and baseline BP and LDL-C levels;

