- Association between the fact of achieving target LDL-C level at week 12 and baseline BP and LDL-C levels as well as CV risk category;
- Association between the fact of achieving target BP and LDL-C levels at week 12 with the categories of CV risk, initial dosage of SPC amlodipine/atorvastatin/perindopril and adherence rate to the administered therapy with FDC.
- Association between patients' adherence to SPC amlodipine/atorvastatin/perindopril therapy at week 4 and week 12 and baseline BP level.
- Predictors for achieving target BP levels (i.e. smoking, sex, baseline SBP and DBP, duration of HTN, level of CV risk, duration of therapy, baseline LDL-C level, CAD diagnosis);
- Predictors for achieving target LDL-C levels (i.e. smoking, sex, baseline SBP and DBP, duration of HTN, level of CV risk, duration of therapy, baseline LDL-C level, CAD diagnosis).

2. Methods and documentation

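### Adherence is reported as adherence to the single-pill combination (SPC), but the scale asks about medication in general and no adherence variable depends on whether the patient is still on the SPC

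*Combined protocol and SAP*

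**What the plan says.** **The construct is specific to the product.** The objective in 1.2 is "To evaluate the adherence to treatment with the fixed dose combination (FDC) of amlodipine/atorvastatin/perindopril in patients included into the study". Section 1.3 turns this into "Proportion of patients with high, moderate and low adherence to the treatment with SPC of amlodipine/atorvastatin/perindopril at V1 as compared to V0", with a matching variable for V2. It also lists "Association between patients' adherence to SPC amlodipine/atorvastatin/perindopril therapy at week 4 and week 12 and baseline BP level", and a further association between reaching the BP and LDL-C targets and adherence to the combination. The data collection lists in 2.7.4 describe the procedure as "assessment of adherence to SPC amlodipine/atorvastatin/perindopril done by medication adherence scale".

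**The instrument is general.** Item 1 of Appendix 2 begins "Sometimes I can make a break in my daily medication therapy for". Item 2 asks how regularly medicines are taken, item 3 about altering the prescribed dose or frequency, and item 4 about when the patient stops. Option 4c is "Medication is withdrawn by the doctor". No item names the SPC, and nothing in the appendix tells the patient to answer for the SPC alone. No points or cut-offs are given for the three adherence levels.

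**SPC status is collected but not used here.** Table 1 (2.7.2) has a row "Treatment with the SPC amlodipine/atorvastatin/perindopril status", marked at V0, V1 and V2, as is the scale. Section 2.5.2 allows other drugs and changes of treatment during follow-up. The only denominator rule, in 4.2, is that a rate includes the patients with an available value.

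**The concern.** The variable is named for one product and the questionnaire measures behaviour across all of a patient's medicines. The two agree only while the SPC is part of the regimen and is taken like the rest of it. They part when a patient leaves the SPC but stays in the study on other tablets, because the scale then describes those tablets and the result is still tabulated under the SPC.

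The introduction (1.1) gives better adherence with a single pill as part of the rationale for the product, so this figure is likely to be cited. If it cannot separate use of the SPC from regular use of something else, it does not answer the objective in 1.2. The associations of adherence with baseline BP and with target attainment would carry the same mixture.

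**Working it through.** The plan states no adherence rate, score or stop rate, so there is no figure to reproduce. The check compares the provisions and then shows what would determine the size.

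**Step 1: follow one patient through the plan.** The doctor switches the patient from the SPC to separate tablets after V1, and the patient takes them every day.

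- Does the patient stay in the study? Section 2.5.2 permits the change, and no rule ends follow-up because of it.
- Is the scale scheduled at V2? Yes; Table 1 makes no exception by SPC status.
- Which answers are truthful? 1d (no breaks), 2a (daily), 3d (dose as prescribed however the patient feels) and 4c (stops when the doctor withdraws the medicine). In each item this is the one option that describes neither irregular use nor a deviation chosen by the patient.
- Does any rule remove or reclassify the result? None in 1.3 or 4.2. The value is available, so the patient enters the denominator.

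The plan as written can therefore place this patient in an SPC adherence category. Which category cannot be derived without a scoring key.

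**Step 2: what sets the size and direction.** Let f be the share of assessed patients off the SPC, h1 the share scored *high* among those on it, and h0 the share scored *high* among those off it.

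Reported share = (1 − f) × h1 + f × h0

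Difference from the on-SPC share = f × (h0 − h1)

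All values below are assumptions; the documents give none of them.

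| f | h1 | h0 | Reported share | Difference from h1 |
|---|---|---|---|---|
| 5% | 60% | 100% | 0.95 × 0.60 + 0.05 × 1.00 = 62.0% | +2 points |
| 10% | 60% | 100% | 0.90 × 0.60 + 0.10 × 1.00 = 64.0% | +4 points |
| 20% | 60% | 100% | 0.80 × 0.60 + 0.20 × 1.00 = 68.0% | +8 points |
| 20% | 70% | 70% | 0.80 × 0.70 + 0.20 × 0.70 = 70.0% | 0 |
| 20% | 70% | 30% | 0.80 × 0.70 + 0.20 × 0.30 = 62.0% | −8 points |

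The sign follows h0 − h1. If most patients off the SPC were switched by the doctor and take the new tablets regularly, the figure rises. If most stopped on their own initiative and say so, it falls. For scale, 5% and 20% of the 274 completed cases in 2.2 are about 14 and 55 patients.

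**The case against.** The strongest reply has four parts.

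- **The misclassification is not certain.** Without points or cut-offs, no answer pattern can be assigned a level. Patients who stop on their own initiative can record breaks, irregular use or stopping in items 1, 2 and 4 (4a, 4b, 4d). This stands. It limits the point to what could happen, most clearly after a switch made by the doctor.
- **The procedure may be meant for the SPC only.** Section 2.7.4 describes the assessment as one of SPC adherence, so a site might skip the scale for a patient no longer prescribed it. That is possible, but neither Table 1 nor Appendix 2 says so, and sites could differ.
- **Adherence is not persistence.** A patient whose doctor withdraws the SPC has followed instructions, and adherence among patients still on the drug is a legitimate measure. This stands, and it is why stopping should not be counted as the lowest adherence level.
- **The stakes are limited.** These are secondary variables in an analysis that 4.2 calls descriptive and exploratory. Non-inclusion criterion 3 keeps other ACE inhibitors, calcium channel blockers, ARBs and statins out at entry, and SPC status is already recorded. This lowers the weight. It does not supply the missing rule, and 2.5.2 allows later changes.

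A reader might go further and infer that both ways of handling stopped patients favour the SPC, or that adherence is overstated by 3.5 to 14 points. The last row of the table contradicts the first inference. The second comes from 0.70 × 0.95 = 66.5% and 0.70 × 0.80 = 56.0%, set against 70%. That calculation gives patients on the SPC the same 70%, so their adherence is not misstated. The gap appears only on moving to a combined measure (still on the SPC and highly adherent), which the protocol does not state, and both inputs are assumed.

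**Conclusion.** The mismatch is established from the documents: the endpoint is specific to the SPC, the scale is not, and no rule connects the adherence category to SPC status. A patient switched from the SPC by the doctor could be classified as adherent to it and enter the proportions and associations.

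A reader might also infer that such a patient is certain to be reported as highly adherent, or that stopping the SPC never lowers the score. The documents support neither, for want of a scoring key and because self-initiated stopping can be recorded.

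The size and direction are unknown. The range of −8 to +8 points in the working rests wholly on assumed stop rates and scores. The point affects secondary variables only, but it deserves correction because the remedy costs almost nothing and lets the endpoint answer its own objective.

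**What to change.** Leave the questionnaire unchanged. In 1.3 and 4.2:

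1. Report the V1 and V2 high, moderate and low proportions among patients recorded as on the SPC at that visit. Show *SPC stopped* as a separate category over all enrolled patients with known SPC status.
2. Report the proportion still on the SPC at V1 and at V2 as its own line, because step 1 alone describes only those who continued.
3. Restrict the association analyses that use adherence to patients on the SPC. Do not count *SPC stopped* as lowest adherence.
4. Label the scale result as general medication adherence, since patients on other medicines answer for the whole regimen.
5. State the scoring key and cut-offs for the three levels, without which the table cannot be built.

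The cost is endpoint and analysis wording and one extra cross-table, using data already scheduled in Table 1. The reported figure may turn out less favourable.
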